### 10.5 Measures to Minimize Bias

### 10.5.1 Enrollment/Randomization/Masking Procedures

Enrollment will not be randomized. Each patient will serve as an internal control.

### 10.5.2 Evaluation of Success of Blinding

Blinding is not possible and not indicated for this study design.

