### 2.4 Potential Risks & Benefits

### 2.4.1 Known Potential Risks

There are no additional potential risks pertaining to this study involving with the use of the Arthrex NanoScope compared to conventional wrist arthroscopy instruments. The NanoScope will be used with the standard extremity stabilization tower and arthroscopic portals as are used with conventional instruments. The diagnostic arthroscopy using the NanoScope will be performed immediately prior to the diagnostic arthroscopy with the conventional instrumentation. Estimated additional time to perform the diagnostic arthroscopy with the NanoScope is < 5 minutes, which will not result in subjects exposure to risks associated with prolonged anesthesia or surgery. There is also no additional wrist of passing a second device (NanoScope) into the wrist joint, in addition to the conventional arthroscope.

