### 4.2 Study Endpoints

### 4.2.1 Primary Study Endpoints

The primary endpoint will be diagnostic accuracy (%) compared to the gold standard of conventional wrist arthroscopy instruments.

The primary endpoint was chosen to determine if smaller instrumentation provides adequate visualization for the diagnosis of wrist pathology and can therefore be used as the sole means of evaluation.

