### 6.3.2 Procedures for Training of Clinicians on Procedural Intervention

The intervention will be standardized by having a single operator (attending) perform the diagnostic arthroscopy with the Arthrex NanoScope and conventional instruments. The diagnostic arthroscopy will be performed in a stepwise manner evaluating the ligaments and articular surfaces of the wrist.

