# 7.1 Study Procedures/Evaluations

### 7.1.1 Study Specific Procedures

- Patients undergoing wrist arthroscopy for diagnostic evaluation and treatment of a wrist injury will be enrolled pre-operatively following a
  discussion of the study, risks, benefits, and informed consent.
- All patients will be positioned supine and placed in an upper extremity traction tower with the shoulder abducted, elbow flexed to 90 degrees, forearm in neutral position.
- Standard arthroscopic portals will be made for viewing, instrumentation, inflow, and outflow: 3-4 portal, 6-R portal, midcarpal ulnar (MCU) portal, +/- midcarpal radial (MCR) portal, +/- 6-U portal.
- A diagnostic arthroscopy will be performed with the Arthrex NanoScope.
  - Structures evaluated:
    - Radial styloid
    - Proximal scaphoid articular cartilage
    - Scaphoid fossa
    - Radioscaphocapitate (RSC) ligament
    - Long radiolunate (LRL) ligament
    - Short radiolunate (SRL) ligament
    - Scapholunate (SL) ligament
    - Proximal lunate articular cartilage
    - Lunate fossa
    - Triangular fibrocartilage complex (TFCC)
  - The attending performing the diagnostic arthroscopy will make an initial diagnostic assessment based on the presence/location/severity of synovitis, articular cartilage integrity, ligament injury and determine the intended treatment.
- A diagnostic arthroscopy will then be performed with the standard arthroscopic instruments.
  - Structures evaluated:
    - Radial styloid
    - Proximal scaphoid articular cartilage
    - Scaphoid fossa
    - Radioscaphocapitate (RSC) ligament
    - Long radiolunate (LRL) ligament
    - Short radiolunate (SRL) ligament
    - Scapholunate (SL) ligament
    - Proximal lunate articular cartilage
    - Lunate fossa
    - Triangular fibrocartilage complex (TFCC)
  - The attending performing the diagnostic arthroscopy will make the final diagnostic assessment based on the presence/location/severity of synovitis, articular cartilage integrity, and ligament injury and determine the final treatment.

Study number: i20-00356 Page 17 Version: June 8, 2020

- Following the procedure the surgeon will perform a short questionnaire.
  - Surgeon rated visualization. (5 point scale)
  - Surgeon-rated ease of use. (5 point scale)
  - o Surgeon-rated diagnostic confidence. (5 point scale)
- The initial diagnostic assessment and final diagnostic assessment will be compared to determine diagnostic accuracy of the Arthrex NanoScope.

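### One unmasked surgeon makes both the NanoScope reading and, straight after, the reference reading, and no rule closes the first entry, so agreement is liable to be inflated and cannot by itself support sole use

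*Combined protocol and SAP*

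**What the plan says.** Section 6.3.2 standardises the procedure by "having a single operator (attending) perform the diagnostic arthroscopy with the Arthrex NanoScope and conventional instruments". Section 2.4.1 fixes order and interval: "The diagnostic arthroscopy using the NanoScope will be performed immediately prior to the diagnostic arthroscopy with the conventional instrumentation". It puts the NanoScope step at under 5 minutes. Section 4.1 names the conventional instruments as the gold standard.

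Section 7.1.1 has the attending make an initial assessment and an intended treatment with the NanoScope, then a final assessment and a final treatment with the conventional scope. It continues: "The initial diagnostic assessment and final diagnostic assessment will be compared to determine diagnostic accuracy of the Arthrex NanoScope". Intended and final treatment are compared in the same way, which gives the change-in-intervention endpoint.

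Section 4.2.1 says the primary endpoint was chosen to find out whether the smaller instrument shows enough and "can therefore be used as the sole means of evaluation".

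On bias, section 10.5.1 says "Enrollment will not be randomized. Each patient will serve as an internal control", and section 10.5.2 says "Blinding is not possible and not indicated for this study design".

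Three places bear on how the first reading is recorded. The Protocol Summary has pathology and intended intervention noted at the NanoScope step and noted again at the conventional step. The Schematic of Study Design lists the NanoScope assessment before the second scope. Section 14.1 requires a correction to leave the original entry legible, initialled and dated, and calls for a Part 11-compliant data capture system.

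**The concern.** An accuracy estimate needs a reference reading that does not depend on the index reading. Here one person makes both within minutes, knowing the first result while making the second. Dependence can enter in two ways:

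- **Anchoring.** A structure called normal through the NanoScope is more readily called normal again, so the reference inherits the miss.
- **Back-revision.** A NanoScope entry that is completed or altered after the conventional look is brought into line with it.

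Both raise agreement and lower the rate of change between intended and final treatment. The within-patient control in section 10.5.1 deals with differences between patients. It does nothing about dependence between two readings by the same surgeon.

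The stake is the question in section 4.2.1. Whether the NanoScope can replace the conventional scope is to be judged from this agreement, and the expected bias runs towards yes. A larger sample would not remove it.

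**Working it through.** **1. What is controlled and what is not.**

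| Element | Provision in the protocol |
|---|---|
| NanoScope findings noted at the NanoScope step | Yes: Protocol Summary, Schematic, 7.1.1 |
| Corrections visible and dated | Yes: 14.1 |
| NanoScope entry complete and closed before the conventional scope | Not stated |
| Time stamp on the NanoScope entry | Not stated |
| Which version is analysed if the entry is changed | Not stated |
| Reference reading independent of the NanoScope reading | No: 6.3.2, 10.5.2 |

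The correction rule applies once an entry exists. It does not stop a first entry from being made after the second look, and it does not say whether the struck-out or the corrected value counts. Section 6.3.3 checks compliance from the medical record and operative report, which need not show when the NanoScope reading was written.

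**2. The plan's own sizing figure.** Section 10.4 uses sensitivity 0.70 against 0.90, prevalence 90%, 31 injured and 34 in total. With an exact binomial rule, n = 31 and 0.025 in each tail:

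- The upper critical value is 27 of 31, and P(X ≥ 27 | 0.70) = 0.0239.
- Adding the lower region (16 or fewer) gives a total size of 0.048.
- Power is P(X ≥ 27 | 0.90) = 0.807.
- The total is 31/0.90 = 34.4.

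This reproduces the row in the section 10.4 table (0.807, 0.048, 31, 34). The power of 0.819 listed in the text of 10.4 differs from that row; nothing below depends on it.

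**3. Illustration of carry-over.** Assume that true NanoScope sensitivity is 0.70 and that a share k of NanoScope misses is carried over. The documents give no value for k; 0, 0.25 and 0.50 are assumptions. The answer depends on the denominator.

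*(a) Anchoring, 31 reference-positive patients.* Carried-over misses become reference-normal, so apparent sensitivity is 0.70 / (0.70 + 0.30(1 − k)):

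- k = 0.25: 0.70/0.925 = 0.757
- k = 0.50: 0.70/0.85 = 0.824

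The rule of 27 of 31 is then applied.

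*(b) Anchoring, 31 truly injured patients.* Carried-over misses leave the denominator. Detected cases are X ~ Bin(31, 0.70), and each of the 31 − X misses stays reference-positive with probability 1 − k. The expected denominator is 31 × 0.925 = 28.7 at k = 0.25 and 31 × 0.85 = 26.4 at k = 0.50. The exact upper-tail 0.025 critical value is taken at each realised denominator (for example 25 of 28).

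*(c) Back-revision.* Misses are rewritten as detections, so apparent sensitivity is 0.70 + 0.30k, which is 0.775 and 0.85, with n = 31.

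Chance of concluding that sensitivity exceeds 0.70 when it does not:

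| k | (a) | (b) | (c) |
|---|---|---|---|
| 0 | 2.4% | 2.4% | 2.4% |
| 0.25 | 9.6% | 5.9% | 14.2% |
| 0.50 | 34% | 20.4% | 49.4% |

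The three columns agree in direction and differ in size by a factor of about 2.4 (14.2/5.9 and 49.4/20.4). A figure quoted without its denominator would mislead.

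**The case against.** The case for the plan has real substance.

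- **Recording is ordered.** NanoScope notation comes first and corrections must remain visible. A reader might infer that the first reading is not recorded at all, or that it can be silently overwritten. The documents do not support that. The gap is narrower: completion before the second look, a time stamp, and a statement of which version is analysed.
- **The order is protective.** With the NanoScope first, the index reading is formed before the reference is seen. This stands, provided the entry is not completed or changed later.
- **A single operator is a deliberate choice.** It avoids differences between surgeons, and an operator cannot be masked to the instrument in hand. Both are true, but closing the first entry needs no masking, no second reader and no change of order.
- **The direction is not certain.** A second look guided by the first could find more lesions and lower apparent NanoScope sensitivity. Inflation is the likelier direction, not an established fact.
- **No test against 0.70 is planned.** Section 10.4 names descriptive statistics and section 10.3.2 reports a percentage. The 0.70 is only the sizing benchmark, so a reader should not infer that a specified test loses its error control. The bias in the reported percentage does not depend on any test.
- **Section 4.2.1 poses a question.** It does not say that agreement would prove sole use. It does make this agreement the means of deciding.
- **A lock is only a partial cure.** It stops back-revision and leaves anchoring untouched. This stands in full and is why the wording of the conclusion also has to change.

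**Conclusion.** The concern holds as a limited and inexpensive correction. The same unmasked surgeon makes both readings in immediate succession, the first entry is not required to be closed before the second, and the analysed version is not named. Agreement is liable to be overstated and the change-in-intervention rate understated. The reference reading is not independent, so agreement alone cannot answer the sole-use question in section 4.2.1.

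The size is unknown from the documents. Under the anchoring assumptions above, the chance of wrongly exceeding the 0.70 benchmark goes from 2.4% to between 5.9% and 9.6% at k = 0.25, and to between 20.4% and 34% at k = 0.50, depending on whether 31 counts truly injured or reference-positive patients. These are illustrations that rest on an assumed k and a true sensitivity of 0.70. They do not estimate the bias in this study.

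**What to change.** 1. **Section 7.1.1.** Require the NanoScope diagnosis for each listed structure, and the intended treatment, to be recorded, time-stamped and closed before the conventional scope is introduced. State that this original entry is the one analysed and that later changes are logged under section 14.1. This removes back-revision only. It has to be in place before enrolment, because the formal SAP promised in section 10.1 cannot recover an entry that was never closed.
2. **Sections 4.2.1 and 10.3.2.** Describe the primary result as same-surgeon, unmasked agreement with conventional arthroscopy. State that it cannot by itself support sole use, because the reference reading is not independent.
3. **Optional.** If a carry-over table accompanies the primary result, label k as an assumption and state the denominator.

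The cost is protocol and form wording, slightly more form work in theatre, and a more cautious stated conclusion. No extra reader, patient or change of order is needed.

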### 10.5.3 Breaking the Study Blind/Participant Code

Not applicable.

## 11 Source Documents and Access to Source Data/Documents

Access to study records will be limited to IRB-approved members of the study team. The investigator will permit study-related monitoring, audits, and inspections by the IRB/EC, the sponsor, government regulatory bodies, and University compliance and quality assurance groups of all study related documents (e.g. source documents, regulatory documents, data collection instruments, study data etc.). The investigator will ensure the capability for inspections of applicable study-related facilities (e.g. pharmacy, diagnostic laboratory, etc.).

Participation as an investigator in this study implies acceptance of potential inspection by government regulatory authorities and applicable University compliance and quality assurance offices.

# 12 Quality Assurance and Quality Control

QC procedures will be implemented beginning with the data entry system and data QC checks that will be run on the database will be generated. Any missing data or data anomalies will be communicated to the site(s) for clarification/resolution.

Following written SOPs, the monitors will verify that the clinical trial is conducted and data are generated, documented (recorded), and reported in compliance with the protocol, GCP, and the applicable regulatory requirements (e.g., Good Laboratory Practices (GLP), Good Manufacturing Practices (GMP)).

The investigational site will provide direct access to all trial related sites, source data/documents, and reports for the purpose of monitoring and auditing by the sponsor, and inspection by local and regulatory authorities.

# 13 Ethics/Protection of Human Subjects

### 13.1 Ethical Standard

The investigator will ensure that this study is conducted in full conformity with Regulations for the Protection of Human Subjects of Research codified in 45 CFR Part 46, 21 CFR Part 50, 21 CFR Part 56, and/or the ICH E6.

Version: June 8, 2020

### 13.2 Institutional Review Board

The protocol, informed consent form(s), recruitment materials, and all participant materials will be submitted to the IRB for review and approval. Approval of both the protocol and the consent form must be obtained before any participant is enrolled. Any amendment to the protocol will require review and approval by the IRB before the changes are implemented to the study. All changes to the consent form will be IRB approved; a determination will be made regarding whether previously consented participants need to be re-consented.

### 13.3 Informed Consent Process

### 13.3.1 Consent and Other Informational Documents Provided to Participants

Consent forms describing in detail the study agent, study procedures, and risks are given to the participant and written documentation of informed consent is required prior to starting intervention/administering study product. The consent materials are submitted with this protocol.

### 13.3.2 Consent Procedures and Documentation

Informed consent is a process that is initiated prior to the individual's agreeing to participate in the study and continues throughout the individual's study participation. Informed consent will occur in the office visit when surgery is indicated/scheduled or in the pre-operative area on the day of surgery. If informed consent is obtained the day of surgery, it will occur in the pre-operative area where informed consent for the procedure occurs, providing a privacy. Patients will be given sufficient time to determine their involvement. Informed consent for surgery is obtained 30 minutes to 1 hour prior to the procedure. Discussion of the study will occur at the same time. If the patient does not feel that they have had enough time to contemplate involvement, they will not be included in the study. Only patients who are comfortable with involvement and express that they have had sufficient time to consider involvement will be asked to sign the consent. Extensive discussion of risks and possible benefits of participation will be provided to the participants and their families. Consent forms will be IRB-approved and the participant will be asked to read and review the document. The investigator will explain the research study to the participant and answer any questions that may arise. All participants will receive a verbal explanation in terms suited to their comprehension of the purposes, procedures, and potential risks of the study and of their rights as research participants. Participants will have the opportunity to carefully review the written consent form and ask questions prior to signing. The participants should have the opportunity to discuss the study with their doctor or relatives or think about it prior to agreeing to participate. The participant will sign the informed consent document prior to any procedures being done specifically for the study. The participants may withdraw consent at any time throughout the course of the trial. A copy of the signed informed consent document will be given to the participants for their records. The rights and welfare of the participants will be protected by emphasizing to them that the quality of their medical care will not be adversely affected if they decline to participate in this study.

A copy of the signed informed consent document will be stored in the subject's research record. The consent process, including the name of the individual obtaining consent, will be thoroughly documented in the subject's research record. Any alteration to the standard consent process (e.g. use of a translator, consent document presented orally, etc.) and the justification for such alteration will likewise be documented.

### 13.4 Posting of Clinical Trial Consent Form

Not applicable.

Version: June 8, 2020

### 13.5 Participant and Data Confidentiality

Information about study subjects will be kept confidential and managed according to the requirements of the Health Insurance Portability and Accountability Act of 1996 (HIPAA). Those regulations require a signed subject authorization informing the subject of the following:

- What protected health information (PHI) will be collected from subjects in this study
- Who will have access to that information and why
- Who will use or disclose that information
- The rights of a research subject to revoke their authorization for use of their PHI.

In the event that a subject revokes authorization to collect or use PHI, the investigator, by regulation, retains the ability to use all information collected prior to the revocation of subject authorization. For subjects that have revoked authorization to collect or use PHI, attempts should be made to obtain permission to collect at least vital status (i.e. that the subject is alive) at the end of their scheduled study period.

Paper consent forms will be kept in a designated file box in the principal investigators locked office.

All study data will be collected, organized and stored on a safe, MCIT managed network drive. A "key" file will be created associating the MRN to a numerical value (1, 2, 3...). Once the data collection portion of the study is complete, all data sheets will be de-identified by permanently removing the "key" file containing identifiable information from the database (MRN).

The study database will only be accessed by the principal investigator and sub-investigators.

Study data will be stored for no fewer than 3 years after completion of data collection to ensure appropriate time for data analysis, as well as need for re-review in analysis, write-up, publication and peer-review processes.

### 13.6 Future Use of Stored Specimens

Not applicable.

# 14 Data Handling and Record Keeping

### 14.1 Data Collection and Management Responsibilities

Data collection is the responsibility of the clinical trial staff at the site under the supervision of the site PI. The investigator is responsible for ensuring the accuracy, completeness, legibility, and timeliness of the data reported.

All source documents should be completed in a neat, legible manner to ensure accurate interpretation of data. Black ink is required to ensure clarity of reproduced copies. When making changes or corrections, cross out the original entry with a single line, and initial and date the change. DO NOT ERASE, OVERWRITE, OR USE CORRECTION FLUID OR TAPE ON THE ORIGINAL.

Copies of the electronic CRF (eCRF) will be provided for use as source documents and maintained for recording data for each participant enrolled in the study. Data reported in the eCRF derived from source documents should be consistent with the source documents or the discrepancies should be explained and captured in a progress note and maintained in the participant's official electronic study record.

Version: June 8, 2020

Clinical data (including AEs, concomitant medications, and expected adverse reactions data) and clinical laboratory data will be entered into a 21 CFR Part 11-compliant data capture system. The data system includes password protection and internal quality checks, such as automatic range checks, to identify data that appear inconsistent, incomplete, or inaccurate. Clinical data will be entered directly from the source documents.

### 14.2 Study Records Retention

Study documents will be retained for the longer of 3 years after close-out, 5 years after final reporting/publication, or 2 years after the last approval of a marketing application is approved for the drug for the indication for which it is being investigated or 2 years after the investigation is discontinued and FDA is notified if no application is to be filed or if the application has not been approved for such indication. No records will be destroyed without the written consent of the sponsor, if applicable. It is the responsibility of the sponsor to inform the investigator when these documents no longer need to be retained.

